7.2 Evaluation of Safety

Safety will be measured by adverse events reported to the investigators by participants, laboratory test results, and clinical evaluation. Toxicity will be assessed according to the NCI CTCAE version 5.0. Safety analyses will be performed for all participants who have completed at least one dose of treatment and will encompass the duration of each participant's study treatment and until 30 days after last treatment. Please see [Section 8.1.3](#) for further details on safety analysis.

Any clinically relevant toxicity (\geq grade 3 hematologic adverse events or any grade non-hematologic adverse events) as determined by the treating provider thought to be probably, possibly, or definitely related to daratumumab, azacitidine, or dexamethasone exposure should be reported. Any clinically significant abnormalities persisting at the end of the study/early withdrawal will be followed by the investigator until resolution or until a clinically stable endpoint is reached.

Overview

As the sponsor of the Study, Principal Investigator shall be solely responsible for complying, within the required timelines, any safety reporting obligation to competent Health Authorities, IRB/ECs and any participating (co or sub) investigators, as defined in applicable laws and regulations. For the purposes of this section, safety data includes adverse events, product quality complaints (PQCs), and special situations including pregnancies.

Principal Investigator will provide safety information to Janssen Scientific Affairs, LLC on adverse events, special situations including pregnancies and product quality complaints as defined within this section.

Management of Safety Data

This Study has been designated as an interventional study. As such, all adverse events, special situations including pregnancies and product quality complaints will be reported as described in this exhibit from the time a subject has signed and dated an Informed Consent Form (ICF) until 30 days after the last documented use of a product under study within the study. All subsequent AEs and SAEs will be collected after this period if the Principal Investigator considers the AE/SAE to be causally-related to the use of the study drug.

For the purposes of this study, the J&J medicinal product is: DARZALEX® (daratumumab). The Celgene medicinal product is: VIDAZA™ (azacitidine).

7.3 Definitions of Adverse Events

Adverse Event (AE)

An adverse event is any untoward medical occurrence in a clinical study subject administered a medicinal (investigational or non-investigational) product. An adverse event does not necessarily have a causal relationship with the treatment. An adverse event can therefore be any unfavorable and unintended sign (including an abnormal finding), symptom, or disease temporally associated with the use of a medicinal (investigational or non- investigational) product, whether or not related to that medicinal (investigational or non-investigational) product. (Definition per International Conference on Harmonisation [ICH])

This includes any occurrence that is new in onset or aggravated in severity or frequency from the baseline condition, or abnormal results of diagnostic procedures, including laboratory test abnormalities.

Adverse Events of Special Interest

Adverse events of special interest are events that Janssen Scientific Affairs, LLC is actively monitoring as a result of a previously identified signal (even if non-serious). These adverse events are:

- Administration reactions: \geq grade 3
- Infections: \geq grade 4
- HBV Reactivation
- **Cytopenias: \geq grade 4**
- Other malignancies

Any Adverse Event of Special Interest that is to be reported to Janssen should be recorded on a Serious Adverse Event Report Form and be reported to Janssen within 24 hours of knowledge of the event.

Serious Adverse Events (SAE)

A serious adverse event based on ICH and EU Guidelines on Pharmacovigilance for Medicinal Products for Human Use is any untoward medical occurrence that at any dose:

- Results in death
- Is life-threatening
(The subject was at risk of death at the time of the event. It does not refer to an event that hypothetically might have caused death if it were more severe.)
- Requires inpatient hospitalization or prolongation of existing hospitalization*
- Results in persistent or significant disability/incapacity
- Is a congenital anomaly/birth defect
- Is a suspected transmission of any infectious agent via a medicinal product
- Is medically important**

**Medical and scientific judgment should be exercised in deciding whether expedited reporting is also appropriate in other situations, such as important medical events that may not be immediately life threatening or result in death or hospitalization but may jeopardize the subject or may require intervention to prevent one of the other outcomes listed in the definition above. These should usually be considered serious.

NOTE: DEATH FOR ANY REASON SHOULD BE REPORTED AS A SERIOUS ADVERSE EVENT.

Hospitalization

For reports of hospitalization, it is the sign, symptom or diagnosis which led to the hospitalization that is the serious event for which details must be provided.

Any event requiring hospitalization or prolongation of hospitalization that occurs during the study must be reported as a serious adverse event, except hospitalizations for the following:

- Hospitalizations not intended to treat an acute illness or adverse event (e.g., social reasons such as pending placement in long-term care facility)
- Surgery or procedure planned before entry into the study. [Note: Hospitalizations that were planned before the start of data collection and where the underlying condition for which the hospitalization was planned has not worsened will not be considered serious adverse events. Any adverse event that results in a prolongation of the originally planned hospitalization is to be reported as a new serious adverse event.]
- [For convenience the investigator may choose to hospitalize the subject for the duration of the treatment period.]

Life-threatening Conditions

Disease progression should not be recorded as an adverse event or serious adverse event term; instead, signs and symptoms of clinical sequelae resulting from disease progression/lack of efficacy will be reported if they fulfill the serious adverse event definition.

Unlisted (Unexpected) Adverse Event/Reference Safety Information

An adverse event is considered unlisted if the nature or severity is not consistent with the applicable product reference safety information. For a medicinal product(s) with a marketing authorization, the expectedness of an adverse event will be determined by whether or not it is listed in the applicable product information.

<http://www.darzalex.com/shared/product/darzalex/darzalex-prescribing-information.pdf>

For DARZALEX® (daratumumab), the expectedness of an adverse event will be determined by whether or not it is listed in the Investigator's Brochure, section 6, Reference Safety Information

7.4 Recording of Adverse Events

Refer to the Data Safety Monitoring Plan, located in Appendix 2.

7.5 Follow-up of Adverse Events

All participants who experience adverse events will be followed with appropriate medical management until resolved or stabilized, as determined by the investigator, or until the initiation of new anti-cancer therapy, whichever occurs first. For selected adverse events for which administration of the investigational product was stopped, a re-challenge of the subject with the investigational drug may be conducted if considered both safe and ethical by the investigator.

7.6 Adverse Events Monitoring

Refer to the Data Safety Monitoring Plan, located in Appendix 2.

Adverse events (with the exception of progression of multiple myeloma) will be reported by the subject (or, when appropriate, by a caregiver, surrogate, or the subject's legally acceptable representative) for the duration of the study (ie, from the time a signed and dated informed consent is obtained until 30 days following the last dose of study treatment).

7.7 Expedited Reporting

Reporting to the Data and Safety Monitoring Committee

If a death occurs during the treatment phase of the study or within 30 days after the last administration of the study drug(s) and it is determined to be related either to the study drug(s) or to a study procedure, the Investigator or his/her designee must notify the DSMC Chair (or qualified alternate) within 1 business day of knowledge of the event. The contact may be by phone or e-mail.

Reporting to Institutional Review Board

The UCSF PI must report events to the UCSF IRB according to institutional guidelines.

UCSF IRB website for guidance in reporting adverse events: <https://irb.ucsf.edu/adverse-event>

Expedited Reporting to the FDA

If the study is being conducted under an IND, the Sponsor (or the Sponsor-Investigator) is responsible for determining whether or not the suspected adverse reaction meets the criteria for expedited reporting in accordance with federal regulations (21 CFR §312.32).

The Sponsor (or Sponsor-Investigator) must report in an IND safety report any suspected adverse reaction that is both serious and unexpected. The Sponsor needs to ensure that the event meets all three definitions:

- Suspected adverse reaction
- Unexpected
- Serious

If the adverse event does not meet all three of the definitions, it should not be submitted as an expedited IND safety report.

The timeline for submitting an IND safety report to FDA is no later than **15 calendar days** after the Investigator determines that the suspected adverse reaction qualifies for reporting (21 CFR 312.32(c)(1)).

Any unexpected fatal or life-threatening suspected adverse reaction will be reported to FDA no later than **7 calendar days** after the Investigator's initial receipt of the information (21 CFR 312.32(c)(2)).

Any relevant additional information that pertains to a previously submitted IND safety report will be submitted to FDA as a Follow-up IND Safety Report without delay, as soon as the information is available (21 CFR 312.32(d)(2)).

Interventional IIS Janssen Scientific Affairs Requirements for Safety Data Collection and Reporting

Special Reporting Situations

Safety events of interest for a J&J medicinal product that require expediting reporting and/or safety evaluation include, but are not limited to:

- Drug exposure during pregnancy (maternal and paternal)
- Overdose of a J&J medicinal product
- Exposure to a J&J medicinal product from breastfeeding
- Suspected abuse/misuse of a J&J medicinal product
- Inadvertent or accidental exposure to a J&J medicinal product
- Any failure of expected pharmacological action (i.e., lack of effect) of a J&J medicinal product
- Medication error (includes potential, intercepted or actual) involving a J&J product (with or without patient exposure to the J&J Product(s) under study, e.g., name confusion)
- Suspected transmission of any infectious agent via administration of a medicinal product
- Unexpected therapeutic or clinical benefit from use of a J&J medicinal product

These safety events may not meet the definition of an adverse event; however, from a Janssen Scientific Affairs, LLC perspective, they are treated in the same manner as adverse events. Special situations should be recorded on the Adverse Event page of the CRF.

Any special situation that meets the criteria of a serious adverse event should be recorded on a Serious Adverse Event Report Form and be reported to Janssen Scientific Affairs, LLC within 24 hours of becoming aware of the event.

Individual Case Safety Report (ICSR)

A valid ICSR must contain the four minimum criteria required to meet regulatory reporting requirements.

- an identifiable subject (but not disclosing personal information such as the subject's name, initials or address)
- an identifiable reporter (investigational site)
- a J&J medicinal product
- an adverse event, outcome, or certain special situations

The minimum information required is:

- suspected J&J medicinal product (doses, indication)
- date of therapy (start and end date, if available)
- batch or lot number, if available
- subject details (subject ID and country)
- gender
- age at AE onset
- reporter ID
- adverse event detail (AE verbatim in English), onset date, relatedness, causality, action taken, outcome, (if available)
- J&J protocol ID

Product Quality Complaint (PQC)

A product quality compliant is defined as any suspicion of a product defect related to a potential quality issue during manufacturing, packaging, release testing, stability monitoring, dose preparation, storage or distribution of the product, or delivery system. Not all PQCs involve a subject. Lot and batch numbers are of high significance and need to be collected whenever available.

Examples of PQC include but not limited to:

- Functional Problem: e.g., altered delivery rate in a controlled release product
- Physical Defect: e.g. abnormal odor, broken or crushed tablets/capsules
- Potential Dosing Device Malfunction: e.g., autoinjector button not working, needle detaching from syringe
- Suspected Contamination
- Suspected Counterfeit

Pregnancy

All initial reports of pregnancy must be reported to Janssen Scientific Affairs, LLC by Principal Investigator **within 24 hours of becoming aware of the event** using the Serious Adverse Event Form. Abnormal pregnancy outcomes (e.g. spontaneous abortion, fetal death, stillbirth, congenital anomaly, ectopic pregnancy) are considered serious adverse events and must be reported using the Serious Adverse Event Form.

Any subject who becomes pregnant during the study must be promptly withdrawn from the study and discontinue further study treatment.

Because the effect of the J&J medicinal product on sperm is unknown, pregnancies in partners of male subjects exposed to a J&J medicinal product will be reported by Principal Investigator **within 24 hours of their knowledge of the event** using the Serious Adverse Event Form. Depending on local legislation this may require prior consent of the partner.

Follow-up information regarding the outcome of the pregnancy and any postnatal sequelae in the infant will be required.

Maintenance of Safety Information

All safety data should be maintained in a clinical database in a retrievable format. Principal Investigator shall provide all adverse events, both serious and non-serious, in report format. However, in certain circumstances more frequent provision of safety data may be necessary, e.g. to fulfill a regulatory request, and as such the data shall be made available within a reasonable timeframe at Janssen Scientific Affairs, LLC request.

Procedures for Reporting Safety Data and Product Quality Complaints (PQCs) for J&J Medicinal Products to Janssen Scientific Affairs, LLC

All adverse events and special situations, whether serious or non-serious, related or not related, following exposure to a J&J medicinal product are to be documented by the investigator and recorded in the CRF and in the subject's source records. Investigators must record in the CRF their opinion concerning the relationship of the adverse event to a J&J medicinal product.

All (serious and non-serious) adverse events reported for a J&J medicinal product should be followed-up in accordance with clinical practice.

SAEs, Adverse Events of Special Interest and Special Reporting Situations

All serious adverse events that have not resolved by the end of the study, or that have not resolved upon discontinuation of the subject's participation in the study, must be followed until any of the following occurs:

- The event resolves
- The event stabilizes
- The event returns to baseline, if a baseline value/status is available

- The event can be attributed to agents other than the study drug or to factors unrelated to study conduct
- It becomes unlikely that any additional information can be obtained (subject or health care practitioner refusal to provide additional information, lost to follow-up after demonstration of due diligence with follow-up efforts)

Principal Investigator will transmit all SAEs, Adverse Events of Special Interest and special situations following exposure to a J&J product under study in a form provided by Janssen Scientific Affairs, LLC in accordance with Section 7.3, Transmission Methods, in English **within 24-hours of becoming aware of the event(s).**

In the event the study is blinded, Principal Investigator will submit an unblinded SAE or pregnancy exposure report to Janssen Scientific Affairs, LLC.

All follow-up information for serious adverse events that are not resolved at the end of the study or by the time of patient withdrawal must be reported directly by the Principal Investigator, **within 24 hours becoming aware**, to Janssen Scientific Affairs, LLC using the Janssen Scientific Affairs, LLC Serious Adverse Event Report

All available clinical information relevant to the evaluation of a related SAE, Adverse Events of Special Interest, serious ADR or special situation is required.

- Principal Investigator is responsible for ensuring that these cases are complete and if not are promptly followed-up. A safety report is not considered complete until all clinical details needed to interpret the case are received. Reporting of follow-up information should follow the same timeline as initial reports.
- Copies of any and all relevant extraordinary (not including routine initial or follow-up ICSR submission) correspondences with regulatory authorities and ethics committees regarding any and all serious adverse events, irrespective of association with the J&J Product under study, are to be provided to Janssen Scientific Affairs, LLC using a transmission method in Section 7.4.4.9 within **24 hours of such report or correspondence being sent to applicable health authorities.**

Non-serious AEs

All non-serious adverse events should be reported to Janssen Scientific Affairs, LLC according to the timeframe outlined in the Research Funding Agreement section entitled Reporting of Data.

PQC Reporting

A PQC may have an impact on the safety and efficacy of the product. Timely, accurate, and complete reporting and analysis of PQC information from studies are crucial for the protection of patients, investigators, and Janssen Scientific Affairs, LLC, and are mandated by regulatory agencies worldwide. Janssen Scientific Affairs, LLC has established procedures in conformity with regulatory requirements worldwide to ensure appropriate reporting of PQC information. Lot and/or Batch #s shall be collected or any reports failure of expected pharmacological action (i.e., lack of effect). The product should be quarantined immediately and if possible, take a picture.

All initial PQCs involving a J&J medicinal product under study must be reported to Janssen Scientific Affairs, LLC by Principal Investigator within 24 hours after being made aware of the event. The Janssen contact will provide additional information/form to be completed.

If the defect for a J&J medicinal product under study is combined with either a serious adverse event or non-serious adverse event, Principal Investigator must report the PQC to Janssen Scientific Affairs, LLC according to the serious adverse event reporting timelines. A sample of the suspected product should be maintained for further investigation if requested by Janssen Scientific Affairs, LLC.

Reporting Procedures for Reporting Safety Data and Product Quality Complaints (PQCs) for Non-J&J Medicinal Products

For SAEs, special reporting situations and PQCs following exposure to a non-J&J medicinal product under study, Principal Investigator should notify the appropriate regulatory/competent authority or the manufacturer of that medicinal product (in the absence of appropriate local legislation) as soon as possible.

Transmission Methods

The following methods are acceptable for transmission of safety information to Janssen Scientific Affairs, LLC:

- Electronically via J&J SECURE Email service (preferred)
- For business continuity purposes, if SECURE Email is non-functional:
 - Facsimile (fax), receipt of which is evidenced in a successful fax transmission report
- Telephone (if fax is non-functional).

Please use the contact information and process information provided by Janssen Scientific Affairs, LLC.

8 Statistical Considerations and Evaluation of Results

8.1 Sample Size Determination

This is a single-arm, open-label, 2-stage phase II study designed to evaluate the efficacy of daratumumab in combination with azacitidine and dexamethasone in RRMM patients previously treated with daratumumab. A Simon's two-stage design⁵⁸ will be used for this study. The study will begin with accrual of 6 patients in a safety run-in. Safety monitoring bounds for study termination based on DLTs are described in [Section 8.2.2](#). If the safety stopping bounds are not met, study will continue to accrue more Stage I patients.

Sample size calculation was based on assessing the overall response rate (ORR) using Simon's minimax 2-stage design. Interim analysis for efficacy, using ORR, will be performed when the last patient enrolled to Stage 1 has received at least 2 cycles of treatment.

The overall target sample size of 23 patients is based upon having sufficient information to assess whether combined treatment of daratumumab with azacitidine and dexamethasone increases the ORR in this study population of RRMM patients with prior treatment with daratumumab. Data from ongoing clinical trial evaluating the safety, pharmacokinetics, and efficacy of isatuximab in patients with RRMM previously treated with daratumumab has shown preliminary results of ORR 8% (NCT02514668). Isatuximab is another CD38 monoclonal antibody with similar efficacy to daratumumab in RRMM patients.²⁴ Based on these previous results, for this study we would be interested in detecting an improvement in the ORR from a null rate of 8% to 33% ORR, which is based on the daratumumab-pomalidomide-dexamethasone

combination study in patients with RRMM re-treated with daratumumab.²³ Simon's minimax two-stage design will be used. The null hypothesis that the true response rate is 8% will be tested against a one-sided alternative that the true response rate is higher than 33%. In the first stage, 13 patients will be accrued. If there are 1 or fewer responses in these 13 patients, the study will be stopped. Otherwise, 10 additional patients will be accrued for a total of 23. The null hypothesis will be rejected if 5 or more responses are observed in 23 patients. The design will have a 90% power to reject the null hypothesis, if the true response rate is 33%, at one-sided 5% significance level. Accounting for an approximate 10% drop-out/ineligibility rate, maximum target accrual should not exceed 25 participants.

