2.3 Primary, Secondary, and Exploratory Endpoint(s)

Primary endpoints:

- Rate of overall response (ORR) defined as sCR+CR+VGPR + PR as best response utilizing IMWG Uniform Response Criteria⁵⁵ calculated in the time period from initiation of study treatment until discontinuation of treatment

Secondary Endpoints:

[figure not shown]
- Adverse events, as graded by National Cancer Institute Common Terminology Criteria for Adverse Events (NCI CTCAE version 5.0), assessed from the initiation of study treatment until discontinuation of treatment
- Duration of response (DOR) defined as the duration from the date of initial documentation of a response (PR or better) according to the IMWG criteria to the date of first documented evidence of progressive disease according to the IMWG criteria or death due to PD whichever occurred first.
- Overall survival which is defined from the date of first dose of study treatment to the date of death due to any cause or censored based on the date of last encounter if patient is alive or lost to follow-up.
- Progression-free survival which is defined as the duration from the date of first dose of study treatment to the date of first documented evidence of progressive disease or death, whichever occurs first.
- Change in CD38 surface expression of plasma cells after azacitidine treatment (the CD38 expression of plasma cells pre and post first cycle of azacitidine treatment in this trial will be compared)
- Number of patients who achieve at least 1.5 fold increase in their CD38 expression by flow cytometry after azacitidine treatment
- Correlation of change in CD38 expression after azacitidine treatment to response including depth of response and duration of response

3 Study Design

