A Simon's minimax 2-stage design will be used for this study. The study will have an interim halting for safety analysis after enrollment of 6 patients and an interim halting for efficacy analysis after completion of Simon's Stage I with enrollment of 13 patients. Please refer to [Section 8](#) for further details regarding interim analysis, stopping rules, and statistics supporting this design. Safety monitoring will be done throughout the trial per Study Procedures and Schedule of Events.

Response to treatment will be evaluated according to the International Myeloma Working Group (IMWG) response criteria,⁵⁵via standard indices including SPEP, UPEP, immunoglobulin levels, immunofixation, and free light chain assay, at the end of each treatment cycle during induction and consolidation phase and at the end of every two treatment cycles during maintenance phase. See Section 7 for more details on response measurements. Patients will remain on study until they are unable to tolerate treatment due to toxicities or demonstrate progression. At the time of progression, repeat bone marrow biopsy can be obtained at the discretion of the treating hematologist but will not be required by the study.

The anticipated duration of subject participation in this trial is estimated to be 8 months. Patient accrual is estimated to be 12-18 months. Patients will be followed for one year after the last patient has received the last administration of daratumumab. The anticipated duration of the entire study is 3 years.

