All response categories (CR, sCR, VGPR, PR, and PD) require 2 consecutive assessments made at any time before the institution of any new therapy; CR, sCR, VGPR, PR, and SD categories also require documentation of no known evidence of progressive or new bone lesions if radiographic studies were performed. VGPR and CR categories require serum and urine studies regardless of whether disease at baseline was measurable on serum, urine, both, or neither. Radiographic studies are not required to satisfy these response requirements. Bone marrow assessments need not be confirmed. For PD, serum M component increases of more than or equal to 1 g/dL are sufficient to define relapse if starting M-component is ≥5 g/dL.

Disease progression based on 1 of the laboratory tests alone must be confirmed by at least 1 repeat investigation. Clinical judgment should prevail; however, repeat assessments after 1 to 3 weeks can be used as a general guideline.

^a Presence/absence of clonal cells is based upon the kappa/lambda ratio. An abnormal kappa/lambda ratio by immunohistochemistry or immunofluorescence requires a minimum of 100 plasma cells for analysis. An abnormal ratio reflecting presence of an abnormal clone is kappa/lambda of >4:1 or <1:2.

^b Clarifications to IMWG criteria for coding CR and VGPR in subjects in whom the only measurable disease is by serum FLC levels: CR in such subjects indicates a normal FLC ratio of 0.26 to 1.65 in addition to CR criteria listed above. VGPR in such subjects requires a >90% decrease in the difference between involved and uninvolved FLC levels.

◦ Clarifications to IMWG criteria for coding PD: Bone marrow criteria for PD are to be used only in subjects without measurable disease by M-protein and by FLC levels; “25% increase” refers to M-protein, FLC, and bone marrow results, and does not refer to bone lesions, soft tissue plasmacytomas, or hypercalcemia and the “lowest response value” does not need to be a confirmed value.

Clinical Relapse

Clinical relapse is defined using the definition of clinical relapse in the IMWG criteria.⁵⁵ In the IMWG criteria, clinical relapse is defined as requiring one or more of the following direct indicators of increasing disease or end-organ dysfunction that are considered related to the underlying plasma cell proliferative disorder:

1. Development of new soft tissue plasmacytomas or bone lesions on skeletal survey, magnetic resonance imaging, or other imaging

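### The 90% power holds only if response status is complete for all 13 Stage 1 patients at the futility count, and Section 8.1 allows that count once the last patient has had 2 cycles

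*Combined protocol and SAP*

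**What the plan says.** Section 8.1 sets a Simon minimax design. On Stage 1: "If there are 1 or fewer responses in these 13 patients, the study will be stopped". On the final test: "The null hypothesis will be rejected if 5 or more responses are observed in 23 patients". On its properties: "The design will have a 90% power to reject the null hypothesis, if the true response rate is 33%, at one-sided 5% significance level". The Stage 1 analysis "will be performed when the last patient enrolled to Stage 1 has received at least 2 cycles of treatment". Section 3.1 describes "an interim halting for efficacy analysis after completion of Simon's Stage I with enrollment of 13 patients", and Section 8.3 repeats the 1-of-13 rule.

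The endpoint has a longer horizon. Section 2.3 defines ORR as best response "calculated in the time period from initiation of study treatment until discontinuation of treatment", and Section 7.1 likewise runs it to the end of study treatment. The abstract expects about 8 months of treatment. The notes to Table 7-1 say that all response categories "require 2 consecutive assessments made at any time before the institution of any new therapy". Under the study calendar (Section 6.1), response is assessed on Day 1 of each cycle from Cycle 2.

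Sections 3.1, 8.1 and 8.3 do not say how a patient counts who is still on treatment without a response, or whose partial response (PR) is not yet confirmed, when the Stage 1 count is taken.

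**The concern.** A Simon design gives each patient one final response status and one response probability, the same at both looks. Here the stop decision may be taken before the endpoint is mature. At the 2-cycle minimum the last patient has had about two scheduled post-baseline assessments, Day 1 of Cycles 2 and 3. A response first seen at the second of these is not confirmed by the scheduled visits alone, and a response that would appear later is not visible at all.

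If such patients are counted as non-responders, the count can only be too low. An active regimen could then be stopped for futility because its responses had not yet been recorded, and the real chance of a wrong stop would exceed the planned one.

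**Working it through.** **Inputs.** From Section 8.1: null rate 0.08, alternative 0.33, stop at 1 or fewer of 13, reject at 5 or more of 23. Accrual is 2 to 3 patients per month in Section 8.4; the 12 to 18 months in Section 3.1 implies 23/18 = 1.3 to 23/12 = 1.9 per month. Time to response for this regimen is not given. The only figure found is a median of 2 cycles for azacitidine in MDS (Section 1.2), which is another disease and regimen.

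**Step 1: the plan's own figure.**
- Wrong stop at 33%: 0.67^13 + 13 × 0.33 × 0.67^12 = 0.0055 + 0.0351 = 0.0406.
- Power: sum over x = 2 to 13 of P(Bin(13, 0.33) = x) × P(Bin(10, 0.33) ≥ 5 − x) = 0.9031.
- The same sum at 8% gives a type I error of 0.0302, with a 72.1% chance of stopping at Stage 1.

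The stated 90% reproduces for complete Stage 1 data.

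**Step 2: incomplete Stage 1 data.** Let f be the share of eventual confirmed responders who can be counted at the look. Each Stage 1 patient is a countable responder (probability p·f), a later responder (p·(1 − f)) or a non-responder (1 − p). The stop rule uses countable responders only; the final test uses all responders. With the same f for all 13:

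| f | Power at 33% | Wrong stop at 33% | Type I error |
|---|---|---|---|
| 1.00 | 90.3% | 4.1% | 3.0% |
| 0.95 | 89.5% | 5.2% | 2.9% |
| 0.90 | 88.4% | 6.6% | 2.8% |
| 0.80 | 85.2% | 10.5% | 2.6% |
| 0.70 | 80.3% | 16.1% | 2.3% |
| 0.60 | 73.3% | 23.9% | 1.9% |
| 0.50 | 63.7% | 34.2% | 1.5% |

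Power drops below 90.0% once f is under about 0.98.

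A check without a time-to-response model: suppose the last 3 patients contribute nothing countable and the other 10 are complete. The wrong stop is then 0.67^10 + 10 × 0.33 × 0.67^9 = 0.018 + 0.090 = 10.8%, and power is 85.1%.

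**Step 3: staggered entry.** Earlier patients have more follow-up, so f differs by patient. With the last patient at exactly 2 cycles, a patient followed for T cycles has f = 1 − 0.5^((T − lag)/median). Lag is 0, or 1 cycle if confirmation waits for the next visit. Cycles are taken as 28 days.

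Example: 2.5 patients per month, a 5-week lead-in pause (1.25 cycles), median 2, lag 1. The entry gap is 30.44/2.5/28 = 0.435 cycles.
- Last patient: T = 2, f = 1 − 0.5^(1/2) = 0.29.
- First patient: T = 2 + 12 × 0.435 + 1.25 = 8.47, f = 1 − 0.5^(7.47/2) = 0.92.
- The mean f is 0.69, power is 80.4% and the wrong stop is 16.1%.

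Power over the two accrual plans, with and without the pause:

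| Accrual per month | Median (cycles) | No lag | One-cycle lag |
|---|---|---|---|
| 2 to 3 | 1 | 89% | 87-88% |
| 2 to 3 | 2 | 83-86% | 76-82% |
| 1.3 to 1.9 | 2 | 85-87% | 82-86% |

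Counting only at scheduled monthly visits lowers these by a few points. Requiring all responses to occur within 8 cycles raises them. Allowing for both, at 1.5 to 2.5 patients per month, power is about 86-89% at a median of 1 cycle, 76-87% at 2 and 65-85% at 3.

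**Step 4: a later count.** Waiting until all 13 are resolved is f = 1, which returns 90.3%. Waiting until the last patient reaches 6 cycles gives about 86-90% under the same assumptions, or about 89-90% if responses occur within 8 cycles.

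**The case against.** The strongest reply has four parts.

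- **The trigger is a floor.** The text requires at least 2 cycles for the last of 13 patients; the others will have had more. Two cycles and two efficacy assessments are also what Section 8.2 requires for the response-evaluable population. This stands, and Step 3 credits the longer follow-up. But the plan gives no criterion for waiting beyond the floor, and being evaluable is not the same as having a final response status.
- **The confirmation lag is an assumption.** Table 7-1 sets no minimum interval between the two assessments, so a PR first seen on Day 1 of Cycle 3 could be confirmed by a repeat sample before the analysis. This stands. A reader might infer that the last patient can count only if PR was present on Day 1 of Cycle 2; the documents do not support that as a necessity. Results without the lag are therefore shown.
- **The 90% is correct.** It is, for the stated rule with complete data. A reader might infer that the power is wrong or already lost, or that the protocol should carry a lower figure in its place. The documents do not support that: they give neither a time to response nor a rule that pending patients count as failures. The lowest values need a median of 3 cycles with responses continuing without limit, and nothing in the documents supports either.
- **Waiting has a price.** The longer pause falls when 0 or 1 responses have been confirmed, which is where early futility is most useful. This stands as a cost. It does not affect the go decision, because two confirmed responses settle that at once.

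**Conclusion.** The point holds in conditional form. A binding stop may be taken before a confirmed, whole-treatment endpoint is mature, and the plan has no rule for pending patients. The 90% in Section 8.1 therefore rests on an unstated condition: that all 13 Stage 1 outcomes are complete at the look.

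The size is uncertain. If pending patients count as failures, the loss is 1 to 4 points at a median of 1 cycle, and about 3 to 14 points at 2 cycles (from 90.3% to 87% or 76%). It is larger only if responses are slower still. These figures rest on exponential time to PR, the accrual assumptions above and a look at exactly 2 cycles for the last patient. Type I error is not at issue: it is 3.0% with complete data and lower otherwise. This should be corrected, but it does not invalidate the design or its sample size.

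**What to change.** In Sections 8.1 and 8.3:

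- Open Stage 2 as soon as 2 confirmed responses are seen among the 13.
- Declare futility (1 or fewer of 13) only when each of the 13 has a confirmed response, has progressed or stopped treatment, or has completed a fixed follow-up that the protocol justifies.
- Treat a PR that is unconfirmed at the look as pending, not as a non-response.

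Full resolution keeps the exact Simon rule and its 90.3%. If a cap such as 6 cycles is used, report its operating characteristics with the time-to-response assumption behind them.

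If the 2-cycle look is kept, either state that the 90% assumes complete Stage 1 responses, or define a separate early-response endpoint for Stage 1 and recompute power and type I error for the pair of rules.

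The cost is protocol wording, and a longer accrual pause only when 1 or fewer responses are confirmed at the look. No extra patients are needed and type I error does not rise.
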